1.1. Schedule of Events

Period	SCR ^a	Injection 1 Period									Injection 2 Period									19 EOS/ ET
		2 / BL	3	4	5	6	7	8	9	10 / BL	11	12	13	14	15	16	17	18		
Visit	1																			
Day (D)/Week (W)	N/A	D1	W1	W2	W4	W8	W12	W16	W20	W24 ^b	W25 ^c	W26 ^c	W28	W32	W36	W40	W44	W48	W52	
Window (days) ^d	≤ -28	N/A	±3	±3	±7	±7	±7	±7	±7	±7	±3	±3	±7	±7	±7	±7	±7	±7	±7	
Informed consent	X																			
Inclusion/ exclusion criteria	X	X																		
Demographics and medical history	X	X																		
Vital signs ^e	X	X	X	X	X	X	X	X	X	X	X	X	X	X	X	X	X	X	X	
Height and weight	X																			
Physical examination	X										X								X	
Knee radiograph ^f	X										X								X	
12-lead ECG ^g	X										X							X	X	
Clinical chemistry/ hematology and HbA1c (fasted state)	X ^h	X ⁱ				X				X						X		X	X	
Coagulation Panel	X ^h																			
Serology (HIV/HBV/HCV)	X ^h																			
Urinalysis	X									X								X		
Pregnancy test ^j	X	X								X									X	
Drug screen and alcohol breath tests (onsite)	X	X								X									X	
Morning serum cortisol ^k	X	X	X	X	X	X	X	X	X	X	X	X	X	X	X	X	X	X	X	
Training ^m	X	X					X			X							X			
Daily knee pain diary (NRS) ⁿ										← Record throughout the study →										
WOMAC		X	X	X	X	X	X	X	X	X	X	X	X	X	X	X	X	X	X	
PGIC			X	X	X	X	X	X	X	X	X	X	X	X	X	X	X	X	X	
Randomization		X																		
Synovial fluid aspiration/ Study drug administration		X								X ^o										
Rescue medication ^p										← Review throughout the study →										
Concomitant medications										← Record throughout the study →										
Adverse events										← Record throughout the study →										

Abbreviations: BL = Baseline; D = Day; ECG = electrocardiogram; EOS = End of Study Visit; ET = Early Termination Visit; HbA1c = hemoglobin A1c; HBV = hepatitis B virus; HCV = hepatitis C virus; HIV = human immunodeficiency virus; NRS = numeric rating scale; PGIC = Patient Global Impression of Change; W = Week; WOMAC = Western Ontario & McMaster Universities Osteoarthritis Index.

- a Screening procedures may occur at any time during the Screening period unless otherwise specified. Patients who fail screening because of a mild infectious illness present at the Baseline or Screening, may be rescreened after the infection has resolved with approval of the medical monitor. Documented diagnosis of OA in the index knee can be completed as part of study screening.
- b Patients who cannot attend the Week 24 visit within the visit window because of restrictions resulting from COVID-19, will be encouraged to return to the site before Week 28 to complete the Week 24 visit assessments, if feasible. However, Injection 2 may only be administered within the allowed visit window.
- c These procedures and visits (Week 25 and Week 26) are only required for patients who receive Injection 2 and will take place at **1 and 2 weeks after Injection 2**, respectively.
- d Visit 3 (Week 1) to Visit 19 (Week 52) should occur at the specified time point relative to Visit 2 (Day 1/Baseline), except **Visit 11 (Week 25) and Visit 12 (Week 26)**.
- e Heart rate, respiratory rate, sitting blood pressure, and temperature will be measured after the patient has been in a sitting position for 5 minutes.
- f A posterior-anterior X-ray radiograph will be performed for both knees in standing fixed-flexion (approximately 20 degrees), as applicable. For the Week 24 and Week 52 visits, the posterior-anterior X-ray radiograph may be performed within 14 days before the visit.
- g The 12-lead ECG will be performed after the patient has been supine for at least 5 minutes.
- h If the patient is potentially eligible based on currently available data except laboratory abnormalities, the assessments may be repeated once only to reassess eligibility.
- i Only glucose (fasted state) will be tested in the Visit 2 (Baseline) visit before 9 AM and before study drug administration (Injection 1).
- j Pregnancy tests performed only for women of childbearing potential. Serum pregnancy tests will be performed at Screening; urine pregnancy tests will be performed before dosing at Visit 2 (Baseline/Day 1) and Visit 10 (Week 24, only required for patients receiving Injection 2); and performed at EOS (Week 52) or ET.
- k Serum samples for measurement of cortisol should be collected before 9 AM (and before study drug administration for Injection 1 and Injection 2 at Visit 2 [Day 1] and Visit 10 [Week 24], respectively). A serum cortisol value <5 µg/dL at Screening cannot be retested.
- m Training and assessment of knowledge on pain ratings, allowable rescue medication, and entering data into the diary will be conducted at Screening, Baseline, Week 12, Week 24, and Week 36; and as needed throughout the study.
- n A diary will be used daily to collect responses from patients on index knee pain over the previous 24 hours. Training regarding entering data into the diary will be given. Patients will first be asked to score their average pain in each knee by NRS over the previous 24 hours at the initial Screening visit. After the first Screening visit (Visit 1), the diary must be completed for each knee in the evening daily for at least 5 of the last 7 days of the screening period before returning to the study site for Visit 2 (Day 1/Baseline). After randomization, the patient will record their response on index knee pain in the diary every evening throughout the study until the last day prior to the EOS/ET visit. Sites should monitor patient compliance of diary entries regularly throughout the 52 weeks. If a patient is not compliant, the site should contact the patient as soon as non-compliance is observed.
- o Procedures for those receiving Injection 2. The patient should be checked for the criteria listed in Section 6.6.3 before study drug administration.
- p Initial rescue medication bottle will be dispensed at Screening and as needed. Between Screening and EOS/ET, patients will record the previous 24-hour use of acetaminophen rescue medication daily into the diary. Rescue medication will be reviewed at every study visit.

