8.2. Study Duration

The planned sequence and maximum duration of the study periods for each patient will be as follows:

1. Screening period: up to 4 weeks
2. Injection 1 period: up to 24 weeks following the administration of Injection 1
3. Injection 2 period: up to 28 weeks following the administration of Injection 2

Patients who do not receive Injection 2 will be followed for up to 52 weeks following the administration of Injection 1.

The maximum study duration for each patient is approximately up to 56 weeks.

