8.3.3.3. Visit 10 (Week 24 and Injection 2)

Patients who have completed through Week 24 and meet the Injection 2 criteria (Section 6.6.3) will receive a second injection of blinded study drug (see Section 7.2) at Week 24 (\pm 7 days). Patients who do not receive Injection 2 may remain in the study unless they choose to withdraw or are withdrawn from the study for other reasons.

The following procedures will be performed (Steps 1 through 17 should be completed before study drug administration):

1. Measure vital signs (heart rate, respiratory rate, sitting blood pressure, and temperature) after the patient has been in a sitting position for 5 minutes.
2. Perform physical examination.
3. Collect serum sample for measurement of cortisol before 9 AM.
4. Collect blood samples for clinical chemistry, hematology, and HbA1c in a fasted state.
5. Perform a posterior-anterior X-ray radiograph for both knees in standing fixed-flexion (approximately 20 degrees), as applicable. This may be performed within 14 days before this visit.
6. Perform 12-lead ECG after the patient has been supine for at least 5 minutes.
7. Collect urine sample for urinalysis.
8. For women of childbearing potential, perform urine pregnancy test (β -hCG) before dosing.
9. Perform drug screen and alcohol breath tests (onsite).
10. Review training and assessment knowledge on pain ratings, allowable rescue medication, and entering data into the diary.
11. Review rescue medication use and the diary records. Rescue medication will be dispensed as needed.
12. Record concomitant medications.
13. Record AEs.
14. Complete WOMAC.
15. [REDACTED]
16. Complete PGIC.
17. Confirm if the patient is disqualified from receiving Injection 2 (see Section 6.6.3).
18. Perform synovial fluid aspiration and administer study drug (Injection 2).

19. Investigator to assess patient for AEs after the injection.
20. Ask patients to score their average pain in the index knee for the previous 24 hours by NRS.
21. Ask patients to record their rescue medication use daily in the diary.

8.3.3.4. Visits 11 and 12 (Weeks 25 and 26) – Injection 2 Follow-up Assessments

Patients who receive Injection 2 will return to the clinic for Injection 2 follow-up assessments 1 week (± 3 days) and 2 weeks (± 3 days) after Injection 2. Patients who do not receive Injection 2 will continue with their follow-up assessments as described in Section 8.3.3.5.

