9.3.1.1. Potential for Adrenal Suppression

Transient cortisol reduction is a well described physiologic response in patients who receive IA cortisol injections and should not necessarily be considered an AE. Laboratory evidence of adrenal insufficiency should be assessed in conjunction with clinical signs and symptoms.

Patients and investigators will be educated about symptoms of adrenal insufficiency, and an assessment of clinical signs and symptoms indicating potential adrenal insufficiency will be performed as part of AE evaluation at every visit or contact.

Patients will be provided a wallet card identifying the potential risk for adrenal insufficiency and asked to carry it at all times. This card should include the patient's identifying information, contact information for the investigator, and should note the potential need for emergency glucocorticoid therapy in the setting of shock, surgery, etc.

Morning serum cortisol as measured by the central laboratory will be blinded to the patient, site staff, and blinded study team members (except Screening, Day 1 [pre-dose], and Week 20); results will be reviewed by a separate unblinded medical monitor.

If there is clinical evidence of adrenal insufficiency that may compromise the patient's safety, the investigator should use a local laboratory to obtain a cortisol level or

and/or refer the patient to his or her primary care physician or to an endocrinologist. The investigator may also contact the blinded medical monitor to discuss the patient's case and request review of prior cortisol values.

The unblinded medical monitor will monitor all serum cortisol values. If sustained cortisol suppression is observed beyond 4 weeks following an injection, or any other cortisol values are seen that might appear to compromise patient safety, the unblinded medical monitor may contact

the investigator to review the patient's condition including any potential signs or symptoms of adrenal insufficiency and discuss potential follow-up laboratory testing.

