11.3.4. Safety and Tolerability Analyses

Safety analyses will be conducted using data from the SAF population (as defined in Section 11.2). Safety variables include physical examination, vital signs assessments (heart rate, respiratory rate, sitting blood pressure, and temperature), clinical laboratory assessments (hematology, chemistry, urinalysis), HbA1c, morning serum cortisol, [REDACTED] 12-lead electrocardiogram (ECG), knee radiographs, concomitant medications/therapies, AEs, and signs and symptoms of adrenal insufficiency. Medical history and AEs will be coded using the Medical Dictionary for Regulatory Activities (MedDRA), and concomitant medication will be coded using the World Health Organization Drug (WHODrug) Global Dictionary.

The safety data will be descriptively summarized by treatment group within each injection period. The safety profile following the first and second injections will be evaluated through the examination of the following comparisons:

1. Group A versus Group B for safety data collected following Injection 2.
2. Safety data in Group A, collected following Injection 1 versus Injection 2.

Continuous safety data will be summarized by visit and include changes from baseline (Injection 1 and/or Injection 2 Baseline). Continuous data will also be converted to categorical values where possible (i.e., below, within, and above normal ranges) and summarized in shift from baseline tables. Categorical safety data collected by visit will be summarized showing the counts and percentages in each category at each visit, as well as shifts from baseline as appropriate.

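### Visits 13 to 19 are timed from Day 1, so the Week 28 cortisol sample may fall 28 ±14 days after Injection 2 against 28 ±7 days for Week 4 after Injection 1; assign these samples by actual days since injection

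*Combined protocol and SAP*

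**What the plan says.** **Visit anchor.** Footnote d in Section 1.1 states that Visits 3 to 19 "should occur at the specified time point relative to Visit 2 (Day 1/Baseline), except" Visits 11 and 12. Section 8.3.3.4 times those two visits from the second injection: "1 week (± 3 days) and 2 weeks (± 3 days) after Injection 2". Nothing in the text supplied ties Visits 13 to 19 to Injection 2.

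**Injection 2.** Section 8.3.3.3 says that qualifying patients "will receive a second injection of blinded study drug (see Section 7.2) at Week 24", with ±7 days. Footnote b makes that window a firm limit: "However, Injection 2 may only be administered within the allowed visit window".

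**Cortisol.** Morning serum cortisol is taken at every visit (Section 1.1). Week 4 and Weeks 28 to 52 each carry ±7 days.

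**Uses that depend on time since injection.** Section 9.3.1.1 describes a review by the unblinded medical monitor: "If sustained cortisol suppression is observed beyond 4 weeks following an injection". Section 11.3.4 lists as a planned comparison: "Safety data in Group A, collected following Injection 1 versus Injection 2". The same section summarises continuous safety data by visit, and Section 11.3.4.2 summarises laboratory values by time point.

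**The concern.** The safety of repeat dosing is a secondary objective (Section 5.2), and Section 6.2 acknowledges limited data on repeat injections. The within-Group A comparison is where the trial shows whether a second dose behaves like the first. For cortisol, which changes with time since the injection, that comparison needs samples taken at similar intervals after each dose.

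Injection 1 is given on Day 1, so for Visits 3 to 9 the time since Day 1 is also the time since the injection. After Week 24 the two clocks separate. Visits 11 and 12 follow the injection, but Visits 13 to 19 go back to Day 1. A sample labelled Week 28 can then be about two weeks post-dose in one patient and six weeks in another. In a by-visit summary, this timing variation is mixed with any real difference in recovery after the second dose.

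**Working it through.** The documents state no figure for the interval from Injection 2 to later visits, so there is none to reproduce. What follows is interval arithmetic on the protocol's windows, counted in days from Day 1.

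**Inputs**
- Injection 2: 24 × 7 ± 7 = day 161 to 175 (Section 8.3.3.3).
- Week 28 visit: 28 × 7 ± 7 = day 189 to 203 (Section 8.3.3.5).
- Week 4 visit: 28 ± 7 = 21 to 35 days after Injection 1 (Section 8.3.3.2).

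**Permitted interval, Injection 2 to Week 28**
- Minimum: 189 − 175 = 14 days.
- Maximum: 203 − 161 = 42 days.

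This is 28 ± 14, a spread of 28 days. Week 4 after Injection 1 has a spread of 35 − 21 = 14 days. The same widening applies at each later visit:

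| Visit after Injection 2 | Days since Injection 2 | Matching visit after Injection 1 | Days since Injection 1 |
|---|---|---|---|
| Week 28 | 14–42 | Week 4 | 21–35 |
| Week 32 | 42–70 | Week 8 | 49–63 |
| Week 36 | 70–98 | Week 12 | 77–91 |

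**How often the mismatch would occur** (assumptions; the documents give no distribution of visit dates). Let a and b be the deviations in days of Injection 2 and Week 28 from target. The interval is 28 + b − a, and it lies outside 21 to 35 when |b − a| ≥ 8.
- Independent and uniform on −7 to 7: there are 15 × 15 = 225 pairs. Those outside number 2 × (7 + 6 + 5 + 4 + 3 + 2 + 1) = 56, and 56/225 = 24.9%, or 12.4% on each side.
- Independent normal, SD 3 each: SD of b − a = √(9 + 9) = 4.24. P(|b − a| > 7) = 9.9%; with the cut at 7.5 for whole days, 7.7%.

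**Likely effect on a group mean** (assumptions: uniform dates, and suppression decaying as exp(−t/τ)). The variance of one date is (15² − 1)/12 = 18.67 days². The interval after Injection 2 carries two such terms and the interval after Injection 1 carries one. To second order, the extra term in the mean is ½ × 18.67/τ² × exp(−28/τ). At τ = 14 days, where this is largest, it is ½ × 18.67/196 × exp(−2) = 0.0476 × 0.135 = 0.0064 of the initial suppression. Summing over all date pairs exactly, the maximum over τ is 0.0069. The mean therefore shifts by less than 1% of the initial suppression. The added spread falls mainly on individual values and on proportions by category.

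**The case against.** The strongest reply is that both samples aim at day 28, that 14 and 42 days are extremes, and that on the SD-3 assumption 90 to 92% of Week 28 samples still fall within 21 to 35 days. The Section 11.3.4 comparisons are descriptive. Section 11.2 mentions an analysis visit window without defining it, and Section 11.3 leaves detail to an SAP whose text is not supplied, so injection-based windows may already be planned. All of this stands. It limits the size of the point but does not remove the unequal pairing in the text available.

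A reader might infer more than the documents support:
- **A gap in cortisol monitoring.** Section 9.3.1.1 counts from the injection, not the visit label, and the unblinded medical monitor reviews all values. Week 4 after Injection 1 also straddles 28 days, so the label is no clearer there.
- **Damage to the Week 36 or Week 52 efficacy endpoints.** Section 11.1.1.2 names Week 36 and Week 52, and nothing defines Week 36 as 12 weeks after Injection 2. The FAS includes patients who never receive Injection 2, so a common Day 1 clock is defensible.
- **Bias between arms.** All groups have the same Injection 2 and visit windows, so Group A versus Group B after Injection 2 is on equal terms.
- **Visits out of order.** Visit 13 can precede Visit 12 only if Injection 2 falls on day 173 to 175, Visit 12 is late and Visit 13 early: 10 of 15 × 7 × 15 = 1,575 date combinations, or 0.6% if uniform.
- **A wrong study duration.** Section 8.2 says "Injection 2 period: up to 28 weeks following the administration of Injection 2". The windows permit 357 − 175 = 182 to 371 − 161 = 210 days (26 to 30 weeks), but the stated figure is a nominal planned length.

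**Conclusion.** The point holds as a modest, cheaply corrected weakness in one planned safety comparison. The permitted timing of the Week 28 cortisol sample after Injection 2 is 28 ± 14 days against 28 ± 7 days for its Week 4 counterpart. That follows from the protocol's windows without assumptions. The share of samples outside 21 to 35 days, about 10% to 25%, depends on the assumed distribution of dates. The small effect on means depends on symmetric date variation and an assumed exponential recovery.

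The only analysis affected is the within-Group A comparison of Injection 1 with Injection 2, for cortisol and any other safety measure read by visit.

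**What to change.** Leave the visit schedule and the efficacy timing unchanged. In Sections 11.3.4 and 11.3.4.2 and in the SAP, state the following for patients who receive Injection 2:
- Post-Injection 2 cortisol, and any other safety measure compared between injections, is assigned to analysis windows by actual days since Injection 2. The windows are those applied to days since Injection 1.
- The windows are contiguous, or the values are plotted against actual days, so that no sample is dropped. With cuts at midpoints, for example, (14 + 28)/2 = 21 and (28 + 56)/2 = 42: a sample taken before day 21 joins the 2-week window, while one at day 36 to 42 stays in the 4-week window. The plot shows that late tail.
- A rule says which value is used when two samples fall in one window, since Visit 12 (11 to 17 days after Injection 2) and an early Visit 13 can share one.

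The anchor in footnote d should also be reconciled in wording with the injection-based language of Sections 9.3.1.1 and 11.3.4.

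The cost is a little programming, and some samples will carry a label different from their nominal visit. The dates needed are already collected.

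Re-anchoring Visits 13 to 19 to Injection 2 would also equalise the windows, but at a higher price. Week 36 would then range over 161 + 77 = 238 to 175 + 91 = 266 days from Day 1 (now 245 to 259), and Week 52 over 161 + 189 = 350 to 175 + 203 = 378 (now 357 to 371). That doubles the Day 1 spread of key secondary endpoints 4, 9, 10 and 12 and splits the schedule by receipt of Injection 2. The analysis route avoids both.

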11.2 Analysis Populations		
11.3.1.2. Protocol Deviations		

AMENDED PROTOCOL

The following are the amended protocol and appendices, including all revisions specified above.

3. LIST OF ABBREVIATIONS AND DEFINITION OF TERMS

ABBREVIATION	EXPLANATION
ACR	American College of Rheumatology
ADL	Activities of Daily Living
AE	adverse event
AEAI	AE which is a potential symptom or sign of adrenal insufficiency
AESI	AE of special interest
ANCOVA	analysis of covariance
AUC	area under the time-concentration curve
β-hCG	human chorionic gonadotropin, beta subunit
BOCF	baseline-observation-carried-forward
CFR	Code of Federal Regulations
CIA	collagen-induced arthritis
CRA	clinical research associate
CSR	clinical study report
DSP	dexamethasone sodium phosphate
EC	ethics committee
ECG	electrocardiogram
eCRF	electronic case report form
EDC	electronic data capture
EOS	End of Study
ET	Early Termination
FAS	Full analysis set
FDA	Food and Drug Administration
GCP	Good Clinical Practice
HbA1c	hemoglobin A1c
HBV	hepatitis B virus
HCV	hepatitis C virus
HIV	human immunodeficiency virus
IA	intra-articular
ICF	informed consent form
ICH	International Council for Harmonisation of Technical Requirements for Registration of Pharmaceuticals for Human Use
IEC	independent ethics committee
IND	investigational new drug

ABBREVIATION	EXPLANATION
IRB	institutional review board
IWRS	interactive web response system
JSN	Joint space narrowing
LOCF	last-observation-carried-forward
MAR	missing at random
MCMC	Monte Carlo Markov Chain
MedDRA	Medical Dictionary for Regulatory Activities
MNAR	missing not at random
mPP	Modified Per Protocol
NSAID	Non-steroidal anti-inflammatory drug
NRS	numeric rating scale
OA	osteoarthritis
PGIC	Patient Global Impression of Change
PL	phospholipid
PP	Per Protocol
PT	preferred term
QOL	Quality of life
QTc	QT interval corrected for heart rate
RBC	red blood cell count
SAE	serious adverse event
SAF	Safety population
SAP	statistical analysis plan
SD	standard deviation
SOC	system organ class
TEAE	treatment-emergent adverse event
TLC	Taiwan Liposome Company, Ltd.
ULN	upper limit of normal
US	United States
WOMAC	Western Ontario & McMaster Universities Osteoarthritis Index

4. INTRODUCTION

4.1. Background and Rationale

Osteoarthritis (OA) is a common degenerative joint disorder of the articular cartilage associated with hypertrophic bone changes. Treatment for OA primarily involves a non-pharmacological combination of exercise and lifestyle modification, pharmacological treatment, supplementation with glucosamine or chondroitin sulphate, and surgical joint replacement. Among pharmacological treatments, corticosteroids have both anti-inflammatory and anti-angiogenic properties, and they are routinely given via inject intra-articular (IA) injection for the treatment of chronic knee joint diseases to relieve pain, reduce inflammation, and improve mobility. There are several Food and Drug Administration (FDA)-approved corticosteroids for IA use, including dexamethasone, methylprednisolone, betamethasone, and triamcinolone. However, when effective, the mean duration of benefit may be relatively short, often lasting for only 2 to 4 weeks.¹ Furthermore, repeated injections of corticosteroids may increase the risk of local and systemic side effects, including pericapsular calcification, tendon rupture, skin atrophy/depigmentation, steroid arthropathy, joint infection, facial flushing, hypersensitivity, and hyperglycemia. Common practice is to use IA corticosteroids no more than once every 3 months.

Dexamethasone is a highly potent glucocorticoid whose action is mediated by the binding of the corticosteroid molecule to receptors located within sensitive cells. The physiological function of glucocorticoid is complex and may include a number of mechanisms such as modification of movement and function of leukocytes, reduction of vascular permeability, and reduced prostaglandin synthesis.² TLC599 is a drug product designed to improve the stability of dexamethasone sodium phosphate (DSP) through formulation with the BioSeizer platform technology. DSP is the pro-drug of dexamethasone and has been approved for indications of endocrine disorders, rheumatic diseases, and dermatologic, allergic, or ophthalmic diseases through intravenous or intramuscular administration route. Also, DSP is used to treat the synovitis of osteoarthritis, rheumatoid arthritis or gouty arthritis through IA or soft tissue administration route and keloid, localized inflammation of lichen planus, psoriatic plaques, granuloma annulare or discoid lupus erythematosus may be treated through intralesional administration route. BioSeizer is a proprietary, lipid-based drug delivery system developed by Taiwan Liposome Company (TLC), which can entrap both small molecules and large molecules and then slowly release these therapeutic agents. The release profile of compounds or proteins can be adjusted by modulating the concentration of phospholipids (PLs). By prolonging the local residence time of therapeutic agents, TLC599 in turn reduces treatment frequency and risk to maximize the clinical benefit. Therefore, TLC599 provides an ideal, safe, and long-acting DSP delivery for the treatment in OA.

